Stratification and Random Assignment. A key feature of abstinence incentive programs is that participants tend to clearly dichotomize into responders and non-responders. The former initiate and sustain abstinence early in the program, while non-responders, either never initiate abstinence or do so intermittently or for only short periods of time before relapsing. In this study, participants will be stratified into CM responders versus non-responders based on submission of two consecutive weeks of cocaine-

free urines (6 samples) during study weeks 1- 6. Considerable experience with implementing these types of interventions suggests that there will be close to a 50/50 split between responders and non-responders by the end of the first month of the CM program.

By the end of study week 6, all participants still active in the study (and independent of exactly where they may be in the abstinence-contingent lead-In earnings plan) will be randomly assigned to bupropion vs placebo medication from within the responder vs non-responder strata and introduced to their tailored earnings schedule for the remainder of the study (see graphs below). Those who qualify for relapse prevention by submitting 2 weeks of negative urines will be randomized on the day they submit the 6th negative urine, while those who will clearly not qualify for relapse prevention will be randomized at the start of week 6.

Medication: Bupropion.

[figure not shown]
Commercially available sources of Bupropion XL and Microcrystalline Cellulose (placebo) will be obtained by the BPRU pharmacy. Qualified pharmacy staff will prepare double blind dosages by overencapsulation of bupropion tablets. The inert substance in both active and placebo capsules will be Microcrystalline Cellulose. Active or placebo capsules will be placed in one-week blister pack kits compatible with daily dispensing requirements of the protocol. When a medication order is provided to the pharmacy, the blister packs will be labeled with a subject number and dispensed to the study site. Study medication blister-packs may be dispensed to participants by nursing staff at the methadone clinic dispensary window or by BPRU research staff. Each kit would contain an accountability log for clinic or study staff to document distribution of capsules from the kit to the study participant. Medication will be stored either in a secure vault at the methadone clinic site or in a pharmacy-approved safe within a locked room.

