The aim of this study is to evaluate whether bupropion will enhance cocaine abstinence among methadone-maintained patients who are abusing cocaine. This is being evaluated in a double-blind context. Further, based on evidence that individuals with cocaine use disorder typically present to the clinic with a urine sample that is positive for cocaine (which predicts continued use) or negative for cocaine (which predicts abstinence), we had originally proposed to treat those individuals as two separate groups and run 2 parallel studies (presented as Primary Aims 1 and 2), using contingency management as a background platform to support either abstinence or relapse prevention, respectively. Each aim was intended to enroll 100 individuals (N=200) total, to enable equal distribution of bupropion (n=50) and placebo (n=50) within each aim.

Based on unanticipated difficulties with recruitment, we are now collapsing the two parallel studies into the same overarching study, such that Primary Aim 1 will now be examining the effects of bupropion XL vs. placebo on 24-week abstinence outcomes during and after exposure to a behavioral intervention (CM). We are reducing our sample size to 100 individuals, which still preserves the required 50 participants per medication group that was identified in our power analyses as necessary to detect an effect of the medication. This approach will allow us to achieve our primary aim of determining whether bupropion will enhance cocaine abstinence despite challenges with recruitment and will enable this study to still provide clinically important information to advance the treatment of cocaine use disorder.

We are modifying our statistical plan to accommodate this change in sample size. We will retain the original primary outcome measure (biochemically-confirmed abstinence from cocaine), which will be assessed across all participants (independent of abstinence group) in the same statistical model. The endpoint will be binary (abstinent yes or no), and the treatment effect will be assessed using a repeated-measures logistic regression model having two main effects: medication and time, plus their interaction, as

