well as any necessary covariates, including cocaine positive vs negative urine tests prior to random assignment as a covariate. Generalized linear mixed models (GLMM) will be used to analyze repeated measures data, since this technique can include participants with incomplete data without resorting to imputation. This approach has been found to minimize bias and maximize power in cases of incomplete follow-up (see Hedden et al, 2009). Data will then be examined using the nonbinary method described by McCann and Li (2012) in which participants who meet an end of study threshold of success (1 week EOS abstinence) are assigned values indicating their number of beyond threshold weeks of success (in our case 1-24). This distribution will be analyzed as a function of drug condition using a two-sided Vander Waerden two-sample test (Permutt and Berger, 2000).

All other analyses will be conducted in the overarching group that includes those abstinent and actively using at baseline. This approach will allow us to preserve all study Aims with a reduced sample size that will ensure the study can be completed in the time allowed.

The data analysis plan consists of the following:

- 1) Comparison of groups for baseline differences. Participants will be compared as a function of medication group on baseline characteristics to determine whether they are comparable with respect to general demographic features, baseline drug use, and reinforcement measures (drug vs. money relative reinforcing potency scale, Snaith-Hamilton Pleasure scale). Groups will be compared using t tests for continuous measures and chi-square tests for categorical characteristics. If medication groups are found to differ on baseline measures, then these characteristics will be used as covariates in subsequent analyses assessing treatment effect.
 - 2) Primary outcome analyses: (see above)
- 3) Secondary outcome analyses: The main secondary outcome measure will be biochemically-confirmed abstinence from opiates. We hypothesize that participants receiving bupropion will have a higher proportion of opiate abstinent samples as well as for cocaine. Analyses conducted to assess the treatment effect for opiate use will be identical to those used for cocaine use (described above).

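### At N=100 the plan cannot preserve all aims: 50 per arm was the size required within each of two studies, aims a and b now have about 25 per arm with no planned test, and power for the pooled test is not shown

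*Combined protocol and SAP*

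**What the plan says.** Section 6, under Sample size and power, describes the superseded design as two parallel studies: "Each aim was intended to enroll 100 individuals (N=200) total, to enable equal distribution of bupropion (n=50) and placebo (n=50) within each aim". It then collapses them into one study: "We are reducing our sample size to 100 individuals". The justification offered for the smaller trial is that it "still preserves the required 50 participants per medication group that was identified in our power analyses as necessary to detect an effect". The primary outcome is kept, "which will be assessed across all participants (independent of abstinence group) in the same statistical model". That model has medication, time and their interaction, with pre-randomisation urine status as a covariate. All other analyses are also run in the combined group. The section concludes: "This approach will allow us to preserve all study Aims with a reduced sample size".

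Section 2 (Objectives) still lists two separate hypotheses. Aim a predicts a significant benefit of bupropion among those who reach abstinence in the lead-in, and aim b predicts one among those who do not. The Abstract states the same pair.

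Section 4, under Stratification and Random Assignment, says that participants are "randomly assigned to bupropion vs placebo medication from within the responder vs non-responder strata" and expects that "there will be close to a 50/50 split between responders and non-responders".

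No alpha, target power, effect size, control rate, within-person correlation or dropout allowance is given for any sample size.

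**The concern.** A required sample size belongs to a particular comparison. Here 50 per arm was required for a comparison within one kind of patient, and it was required twice. After the collapse, 50 per arm describes one comparison over both kinds together. The two within-stratum hypotheses remain in the Abstract and Objectives, but each now has about half the participants that the plan itself called necessary, and no analysis in section 6 addresses either of them.

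Two things are at stake. Aims a and b could be reported as if tested at their intended size. And a null pooled result could be presented as adequately powered on the strength of a figure derived for a different comparison.

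**Working it through.** **1. Can the 50 be reproduced?** No. The power analysis is mentioned but none of its inputs is stated. The 50 is taken below as the plan's own requirement.

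**2. Participants per arm per stratum.**
- Two-study design (section 6): 200 / 2 studies / 2 arms = 50.
- Current design, with the even split expected in section 4: 100 × 0.5 / 2 = 25.
- If the split were 60/40: 100 × 0.6 / 2 = 30 and 100 × 0.4 / 2 = 20.

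So aims a and b have about 25 / 50 = one half of the stated requirement. This step needs no assumption about power. It does treat the two groups named in section 6 (by cocaine-positive or cocaine-negative urine) as the lead-in strata defined in section 4, which is how aims a and b are worded.

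**3. What halving does to power.** Assumptions: two-sided 5%, a single comparison of two equal arms, and power of 80% or 90% at 50 per arm. With standardised difference d and n per arm, power = Φ(d√(n/2) − 1.960).
- 80% at 50 per arm: d√(50/2) = 1.960 + 0.842 = 2.802, so d = 0.56. At 25 per arm: 2.802/√2 = 1.981, and Φ(0.021) = 0.51.
- 90% at 50 per arm: 1.960 + 1.282 = 3.242, so d = 0.65. At 25 per arm: 3.242/√2 = 2.292, and Φ(0.332) = 0.63.
- Over 20 to 30 per arm, the ranges are 43% to 58% and 54% to 71%.
- The difference detectable with 80% power rises from d = 0.56 to d = 0.79.

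**4. The pooled test at 50 per arm.** Let f be the average effect over both strata, as a fraction of the effect assumed for the two-study design. Power = Φ(2.802f − 1.960), or Φ(3.242f − 1.960) for the 90% case.

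| Average effect | If 80% was planned | If 90% was planned |
|---|---|---|
| f = 1 (same average effect and variance) | 80% | 90% |
| f = 0.75 | 56% | 68% |
| f = 0.5 (full effect in one stratum, none in the other) | 29% | 37% |

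**5. Cross-check on the binary scale.** This is a single-time-point, stratum-adjusted approximation with 25 per arm per stratum. The odds ratio (3.2 to 3.7) was chosen to give 80% power in one homogeneous group of 50 per arm. Assumed control abstinence rates in responders/non-responders were .5/.3, .6/.2 and .7/.1. With the same odds ratio in both strata, power is 58% to 88%. With an effect in one stratum only, it is 15% to 35%. Pooled power can therefore lie below, near or above the single-study figure, depending on inputs that the plan does not give.

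**The case against.** The sentence on the required 50 directly follows the redefinition of Primary Aim 1 as a pooled comparison. Read in place, it concerns that comparison, which does have 50 per arm, and it claims no power for aims a or b. Section 6 plans no stratum-specific test, so 51% and 63% are the power of tests outside the current plan. The protocol expects benefit in both strata through one dopaminergic mechanism, so an effect confined to one stratum is not its hypothesis. The calculations also assume alpha and power, and use a single comparison where the plan has a repeated-measures model on urines taken three times a week.

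Much of this stands. A reader might infer that the planned power is lost for the pooled test, or that the pooled test is underpowered. The documents do not support that: with the same average effect and variance, power is about unchanged. A reader might also test the 50 against a bupropion-plus-incentives result quoted in section 3 (Background). That result is not given as a design input, and it would bear on whether 50 was ever enough, not on whether it transfers.

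The objection does not rescue the statement on the aims. Sections 1 and 2 still carry both within-stratum hypotheses. If section 6 has replaced them with a pooled question, they have been dropped, not preserved. If they are kept, they have half the required size and no analysis. Nor does expecting benefit in both strata show that the benefit is equal: section 3 poses initiation and relapse prevention as separate questions, and section 4 gives the strata different incentive schedules.

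**Conclusion.** The statement that all aims are preserved at the reduced size is wrong as written. By the plan's own requirement and expected split, aims a and b have about 25 per arm instead of 50. That conclusion rests only on figures in the documents. The fall from 80% to about 51%, or from 90% to about 63%, is illustrative, because the planned power and alpha are assumed.

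For the pooled test the finding is narrower: its power is not shown. It could be what was planned. The figures of 29% and 37% apply only if there is no effect at all in one stratum, and they should not be read as the expected power of the trial.

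**What to change.** - In section 6, delete or qualify the sentence saying that all aims are preserved.
- Reconcile sections 1 and 2 with section 6: label aims a and b as exploratory, estimated with confidence intervals at about 25 per arm.
- Replace the sentence on the required 50 with the power, or the smallest detectable difference, of the pooled repeated-measures model at 50 randomised per arm. State alpha, effect size, control rates by stratum, within-person correlation and dropout allowance. Give the result for an equal effect in both strata and for an effect in one stratum only.

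The cost is a short calculation, edits to three sections, and probably a less favourable stated figure. No extra patients are needed, and the endpoint, the primary model and the allocation are unchanged.

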Placebo is included for scientific validity in a clinical trial needed to answer study questions related to medication efficacy.

f. Definition of treatment failure or participant removal criteria.

There is no clear definition of treatment failure for this study sample of methadone maintained patients since long-term methadone maintenance is standard care for their chronic relapsing disorder. Patients could potentially be dismissed from treatment for violating clinic rules particularly those relating to violence, firearms possession, drug sales or or other unacceptable behavior at the clinic. Participants could be removed from the study if severe or persistent medication side-effects were observed or if new medical conditions developed including pregnancy or concomitant medications were started that made their continued participation unsafe.

g. Description of what happens to participants receiving therapy when study ends or if a participant's participation in the study ends prematurely.

Study participants will continue on usual care methadone maintenance treatment at their normal methadone clinic after the study or in the event of premature withdrawal from the study.

Study Procedures: Urine Testing. Primary outcomes will be based on qualitative (pos/neg) urinalysis testing results using standard detection cut-off values. In order to detect recent use of cocaine, urine samples will be collected three times per week on non-consecutive days throughout the study, usually on Mon, Wed, and Fri. Sample collection will be observed if possible and all samples will additionally be tested for temperature and adulterants. A second sample will be requested if the original sample fails these tampering tests.

Study Procedures: CM Lead-In. Participants will enter the study following an intensive screening during which eligibility is determined, informed consent is signed and baseline assessment is completed. The study itself begins with a 6-week contingency management lead-in during which vouchers can be earned for submission of cocaine negative urine samples under an escalating schedule with reset to the original value in the case of missing or positive urines. A participant who stops cocaine use on the first day of the study and remains continuously cocaine abstinent would earn \$145 by the end of week 6. However, many participants may start earning later than week 1 or experience resets and thus earn less.

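### The only pre-randomisation cocaine-use covariate named for the primary model is an undefined positive/negative term, leaving within-stratum differences recorded by 6 to 18 lead-in urines unadjusted

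*Combined protocol and SAP*

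**What the plan says.** Section 6 (Study Statistics) gives a binary abstinence endpoint analysed by a generalised linear mixed model with medication, time and their interaction. Further covariates are allowed where needed, and one is named: "including cocaine positive vs negative urine tests prior to random assignment as a covariate". The list is open-ended. The urine term is not tied to a particular sample, to the randomisation stratum, or to a count or proportion. Under item 1 of the data analysis plan, other baseline characteristics, including baseline drug use, enter the treatment models only if the medication groups turn out to differ on them.

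Section 4 (Urine Testing) bases the primary outcomes on qualitative urine results and says that "urine samples will be collected three times per week on non-consecutive days throughout the study". Under Stratification and Random Assignment, participants are "stratified into CM responders versus non-responders based on submission of two consecutive weeks"; in practice this is a run of six cocaine-negative samples. Responders "will be randomized on the day they submit the 6th negative urine". For the rest the date is fixed by the calendar: "those who will clearly not qualify for relapse prevention will be randomized at the start of week 6". The outer limit for randomisation is set by "By the end of study week 6, all participants still active in the study". Everyone takes placebo capsules from week 1 under the same lead-in voucher procedure.

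**The concern.** The medication effect is a contrast between people, with 50 per arm. With many urines per person, its main source of noise is how much people differ in underlying cocaine use. The lead-in measures exactly that, repeatedly, with the outcome's own test and before randomisation. A two-category covariate captures part of it and leaves the rest in the residual. Section 6 reports that recruitment difficulty cut the planned sample from 200 to 100, so precision available from data already collected is worth having.

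**Working it through.** **1. The plan's own figure.** The only related number is 50 per medication group, attributed to power analyses. Section 6 gives no alpha, power, effect size, dropout or within-person correlation with it, so it cannot be reproduced, and no figure for covariate precision is stated.

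**2. Scheduled lead-in urines, at 3 per week.**
- Earliest responder: 2 × 3 = 6.
- Clear non-responder, randomised at the start of week 6: 5 × 3 = 15.
- Latest possible: 6 × 3 = 18.

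These are scheduled bounds. Simulated means are about 8 for responders and 15 for non-responders.

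**3. Spread hidden by the stratum.** With 3 samples left in week 6, someone whose current run of negatives is 2 or fewer cannot reach six (2 + 3 = 5). The sequence 5 negative, 1 positive, 5 negative, 1 positive, 2 negative, 1 positive has 12 negatives in 15 and cannot qualify. Someone with 0 negatives in 15 cannot either. The stratum codes both alike.

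**4. Readings of the covariate.**
- *Responder stratum:* summarises the lead-in, but loses the spread in step 3.
- *Last urine:* loses more (see the R² columns below).
- *Presenting urine:* Section 6 describes patients by the urine they present with. The inclusion criteria cite a positive urine at intake or on record in the past 3 months as evidence of current dependence, so this value may vary little.

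**5. Size, under assumptions.** Let ρ be the correlation between a person's propensity to use in the lead-in and after randomisation (assumed; the documents give none). The simulation used 20,000 people per setting, the protocol's randomisation rule, 72 follow-up urines and three assumed distributions of use giving 44% to 50% responders. R² is the share of variance in the follow-up proportion negative that the covariate explains. The multiplier on required N is (1 − R² with proportion) / (1 − R² without), and its reciprocal gives the effective extra participants.

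| Distribution of use | ρ | R² last urine | R² stratum | R² stratum + proportion | N multiplier vs stratum | Extra effective participants |
|---|---|---|---|---|---|---|
| Dichotomous | 0.8 | 0.48 | 0.55 | 0.61 | 0.87 | 15% |
| Bimodal | 0.8 | 0.37 | 0.43 | 0.55 | 0.80 | 25% |
| Normal | 0.8 | 0.28 | 0.33 | 0.47 | 0.80 | 25% |
| Dichotomous | 0.6 | 0.26 | 0.30 | 0.34 | 0.95 | 5% |
| Bimodal | 0.6 | 0.19 | 0.22 | 0.28 | 0.92 | 9% |
| Normal | 0.6 | 0.14 | 0.17 | 0.24 | 0.91 | 10% |

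Example, first row: (1 − 0.61)/(1 − 0.55) = 0.39/0.45 = 0.87, and 1/0.87 = 1.15. Multipliers come from unrounded R². If the stratum-adjusted analysis had 80% power, power with the proportion is Φ(2.80/√multiplier − 1.96): 85% to 88% at ρ = 0.8 and 82% to 84% at ρ = 0.6.

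Two further whole-trial simulations, again against the stratum alone, gave gains of 7–9% and 5–10% at persistence 0.5, and 19–23% and 15–26% at 0.7.

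**6. Check in the planned type of model.** A random-intercept logistic model at N = 100 and ρ = 0.8 gave these empirical SDs of the log odds ratio, for stratum alone and then stratum plus proportion:
- dichotomous: 0.337 and 0.336 (78 replicates);
- bimodal: 0.447 and 0.363 (64 replicates);
- normal: 0.382 and 0.342 (63 replicates).

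The relative error of each SD is about 1/√(2(n − 1)), or 8% to 9%. The check supports a gain in two cases and shows none in the dichotomous case, but fixes neither precisely.

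**The case against.** The covariate list is open and the urine term is plural and undefined, so the text does not firmly commit to one yes/no value. This stands. It means that the covariate needs defining, and that no finer measure is pre-specified.

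The most coherent reading is the responder stratum, since Section 6 merges what had been two parallel studies divided by abstinence status. The stratum is itself computed from the lead-in urines and carries much of their information (R² 0.55 against 0.61 in the dichotomous case, 0.33 against 0.47 in the normal case, ρ = 0.8). A reader might infer that the plan discards the lead-in data. On this reading it does not.

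Section 4 says that participants divide clearly into responders and non-responders, and in that case the gain may be small. The same section, however, describes non-responders as including people with intermittent or short abstinence, so some spread is expected. Non-responders also move to a new voucher schedule and are urged to try again, so high persistence cannot be presumed.

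Lead-in length depends on response, and every responder's series ends in six negatives, so the proportion has unequal denominators. This stands, and it is why the proportion should be added to the stratum and not replace it.

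**Conclusion.** The point holds as one of efficiency. The plan pre-specifies nothing finer than a two-category, undefined measure of use before randomisation, and a continuous lead-in proportion added to the stratum would usually sharpen the medication contrast.

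The gain is roughly 5% to 25% more effective participants over the stratum alone if persistence is 0.5 to 0.8, and possibly close to none if response is sharply dichotomous. The range rests on assumed persistence, assumed distributions of use and the full urine schedule. It concerns the between-person medication effect; a covariate fixed over time does little for the medication-by-time interaction.

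Two stronger inferences are not supported:
- *A large loss.* Set against a single last urine, and in non-responders only, the proportion can look worth 8%, 23% or 72% more participants at persistence 0.5, 0.7 and 0.9 (logit SD 2). The plan never names the last urine as the covariate, those figures cover one stratum, and nothing in the documents supports 0.9.
- *Bias.* Randomisation is within strata and either form of covariate is measured before it, so validity and Type I error are not in question.

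**What to change.** Before unblinding, replace the urine term in Section 6 with two pre-specified covariates in the primary model:
1. the randomisation stratum (responder or non-responder);
2. the proportion of cocaine-negative urines among scheduled lead-in samples, as a continuous variable, from study entry up to and including the last sample before the first dose of randomised medication. This window keeps a responder's qualifying urine.

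State a rule for missing samples, for example the proportion of samples submitted, with missing counted as positive in a sensitivity analysis. Week of qualification need not be added: in simulation it correlated about −0.8 with the responder proportion and added under 1% once the proportion was in the model.

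The cost is wording and one or two degrees of freedom. The urines are already in the collection schedule.
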